To explore the treatment of optic
neuromyelitis with
electroacupuncture(**NMOSD**)The efficacy and
mechanism of pain in patients

Project Source: Postgraduate Project

Research Unit: Guangdong Provincial Hospital of
Traditional Chinese Medicine

Head of Research: [name], [name]

Version number:**6.0**

Version date:**2022.03.01**

1. Program summary

Research topic:	To explore the treatment of optic neuromyelitis spectrum disease by electroacupuncture (NMOSD) Study on the efficacy and mechanism of pain in patients
Purpose of the research	Main purpose: to observe the electrical target NMOSD Secondary purpose of the curative effect of patient pain: Discussion NMOSD The mechanism of pain in patients and the mechanism of electroacupuncture in the treatment of pain in patients with optic neuromyelitis spectrum disease
Research hypothesis	Electroacupuncture can be treated effectively. NMOSD Pain in the patient
Research design	Randomized controlled trial
Test group	Electroneedle group
Control group	False needle group
Sample size	20
Selection Criteria	1 Accord with 2021 Diagnostic criteria for optic poliomyelitis genealogical diseases in China's Guidelines for the Diagnosis and Treatment of optic Neurospinal Myelitis Gene Diseases; 2 NRS \geq 4 Score; 3 Patients use stable doses of biotherapy and/or strong loose, before joining the group 30 There is no adjustment plan within the day; 4 Patients before joining the group 30 No standard drug combinations for pain treatment, including antiepileptic drugs, antidepressants or opioids, were adjusted within the day. 5 The patient or the patient's family sign informed consent. 6 18-80 Year-year-old patient.
Exclusion criteria	1 Patients participating in other clinical studies; 2 Patients with low cognitive or mental ability; 3 People who are pregnant, breastfeed or plan to get pregnant during the study; 4 People with serious diseases related to the heart, liver, kidneys or hematopoietic system; 5 Patients with diabetic peripheral neuropathy.
Test cycle	Total test cycle 30 God, all 18 Visit twice a week.
Outcome evaluation indicators	Main indicators: NRS Mark

	Secondary indicators:EDSS、MPQ Rating, SAS Anxiety Scale, SDS Depression Scale, SF-36 Quality of life scale, IL6、TNF-A、fMRI Target
Safety evaluation indicators	Adverse reactions, blood routine, biochemistry, liver function

2. Research background

The pain is NMOSD A common symptom of the patient. Known as high as 86%Taxi NMOSD Patients will be affected by pain. [3,13,14,15]. A survey on the quality of life and medical experience of Chinese patients shows that pain is the third concern of patients in addition to recurrence and drug side effects, and even more trouble the lives of patients than disability. Weigh 10%The patient believes that the severe pain caused by the disease greatly interferes with normal life. 6%Patients believe that physical pain seriously prevents them from enjoying life.

NMOSD The pain of patients is mainly divided into neuropathological pain and spasm-related pain. Some clinical observations suggest clinical factors.(Such as poliomyelitis and emotions)And demographic factors(Such as age)Give NMOSD Pain-relatedness of patients[3,4,10,11]. At present NMOSD Possible mechanism of pain[32-36] : 1In the physiological state, AQP4 With excitatory amino acid transporter 2 (EAAT2) Common expression, so that astrocytes consume glutamate. AQP4-ab Positive patient's AQP4 In the absence, the intake of glutamate by astrocytes leads to the excessive accumulation of glutamate in the extracellular space, resulting in abnormal excitation of neurons and excitatory tissue damage.2The central nervous system regulates pain mainly from 2 Aspects: Increased excitement and reduction of inhibition. This 2 Each aspect is affected by reactive astrocyte proliferation and its related inflammatory reactions.3Abnormal brain structure: Studies found that the posterior ventral nucleus(VPN) Volume is negatively correlated with a variety of pain intensity indicators. The volume of hippocampus and pale bules in patients with neurological pain is smaller than that of patients with non-nervous pain, and the pain intensity is negatively correlated with the nucleus and thalamus volume.

At present, despite a variety of analgesic drugs and a variety of drug combinations for different pain mechanisms. [12], but there are still 60-80%Taxi NMOSD Patients with moderate and severe pain and completely get rid of pain are less than 10% [3,4]. At the same time, there are many large samples and multiple centers. RCT Research suggests that electroacupuncture is effective in treating pain. [25,26,41,42]. National Institutes of Health(National Institutes Of Health)Estimated, more than 1500 Ten thousand Americans use it.Acupuncture

therapy[27, 28]. The use of electric needles is now recognized by the World Health Organization.[29-31]. The author expounds the analgesic effect of electroacupuncture from the aspects of traditional Chinese medicine and modern medicine. Among them, the design of fake acupuncture is mainly published in BMC Acupuncture study of the same type of disease with pain in the journal[47].

Based on the results of the literature, some progress has been made in the study of electroacupuncture in the treatment of pain, which can be used to regulate inflammatory factors. [16,17,21-23], release analgesic-related factors[19,20,37,39-41], regulate the corresponding brain area[45,46]Activities and other aspects play an analgesic effect.

Therefore, this study hopes to explore the efficacy and related mechanism of electroacupuncture in the treatment of pain in patients with optic poliomyelitis spectrum diseases by comparing the efficacy of electroacupuncture group and the pseudo-acupuncture group. This study assumes that electricity has an effect on pain in patients with optic neuromyelitis spectrum disease, and then verifies the mechanism of electricity on the pain of patients with optic neuromyelitis genealogy diseases for clinical treatment options.

References:

5.1 Selection Criteria

1 Accord with 2021 Diagnostic criteria for optic poliomyelitis genealogical diseases in China's Guidelines for the Diagnosis and Treatment of optic Neurospinal Myelitis Gene Diseases;

2 NRS \geq 4 Score;

3 Patients use stable doses of biotherapy and/or strong loose, before joining the group 30 There is no adjustment plan within the day;

4 Patients before joining the group 30 No standard drug combinations for pain treatment, including antiepileptic drugs, antidepressants or opioids, were adjusted within the day.

5 The patient or the patient's family sign informed consent.

6 18-80 Year-year-old patient.

5.2 Exclusion criteria:

1 Patients participating in other clinical studies;

2 Patients with low cognitive or mental ability.

3 People who are pregnant, breastfeed or plan to get pregnant during the study;

4 People with serious diseases related to the heart, liver, kidney or hematopoietic system.

5 Patients with diabetic peripheral neuropathy.

5.3 Exclusion criteria:

Incorrectly included in the case;

Subjects took drugs that affected the relevant indicators of this study without authorization;

5.4 Fall off standard:

The subjects failed to complete the treatment as required by the researchers;

The subjects did not cooperate with the arrangement for personal reasons, and the researchers believed that the patient had poor compliance and was not suitable for research;

The subjects withdrew from the study on their own.

6. Sampling estimation and grouping method

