6.1 Estimate of sample size

The spectrum disease of optic neuromyelitis is a rare disease, and this study is an exploratory study. Referring to previous studies, the sample size of this topic is 20 Example.

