6.3 Blind law

The study includes the blind design of patients and evaluators. Only acupuncture operators know. Intervention to be used. The treatment was carried out according to the individual's schedule, so no patient had any contact with other patients in the study. In addition, all patients agree not to contact other participants and avoid talking about their treatment.

7. Interventions

This study is divided into 2 The group is the electric needle group and the false needle group respectively. The place of acupuncture treatment is Department of Neurology, Dade Road Hospital, Guangdong Provincial Hospital of Traditional Chinese Medicine. Every week 2 Times, every time 30 Minutes of electric needles (true or false), continuous 1 Months in total 8 Times (the course of treatment is 30 Oh, my God).

1· Basic treatment and emergency plan

Before starting the designated treatment plan, the patient Accepted NMOSD Guidelines for the remission period (hormonal combined immunosuppressants (immunosuppressants include thiopurine, medicophenol ester or rithitoximab)) and/Accepted NMOSD Guidelines for patients with pain (pribalin, barclofen or

gabapentine), basic treatment during the study and guidelines for patients before grouping. In the next stage of the study, all patients will start their designated treatment plan. (Electric needle) This point in time is set to 1 Day, the treatment period is 30 Oh, my God. Patients record the daily intake and intensity of analgesic drugs required. (NRS) Standardized patient diary of pain parts.

2· Test group: electric needle group

Take acupuncture points: three miles of both feet (ST36), Sanyin sex (SP6), Hegu (LI4) and Quchi (LI11), insert the needle, insert the ninth needle into the seal hall (EX-HN3)

Acupoint location reference 2006 National standards of the People's Republic of China (GB/T12346-2006 Name and Positioning of Acupoints.

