(1) The doctor will ask, record the medical history and the results of previous examinations, conduct a comprehensive physical examination of you, and the nurse will collect the patient. 3ml Blood routine, biochemical, liver function, IL6, TNF- α Examine and take blood samples, tongue coating samples and feces samples, and collect demographic information of subjects through the inpatient medical record system.

(2) Perfect EDSS, NRS Scales, MPQ Pain scale, SDS Depression Scale, SAS Anxiety Scale, SF-36 Quality of life scale.

(3) Perfect and collect head, neck and chest MR Scan and enhance relevant data to improve fMRI Check and collect relevant data.

2. Treatment period:

The electroacupuncture group will be treated with electroacupuncture on the basis of immunotherapy and basic analgesia, and the control group will receive false acupuncture treatment on the basis of immunotherapy and basic analgesia. Every week 2 Times, every time 30 Minutes of electric needles (true or false), continuous 1 Months in total 8 Times (the course of treatment is 30 Oh, my God). Patients fill in a pain diary every day, and the treatment is carried out by the same acupuncturist. The manufacturer and use of acupuncture acupuncture needles, fake acupuncture and electroacupuncture instruments are consistent.

3. Eighth post-treatment visit (group No. 28 ± 3 Day):

(1) Patients collected by nurses 3ml The blood is routinely tested for blood, biochemical and liver function, and blood samples, tongue coating samples and feces samples are retained.

(2) Perfect EDSS, NRS Scales, MPQ Pain scale, SDS Depression Table, SAS Anxiety Scale, SF-36 Quality of life scale.

(3) Perfect fMRI Check and collect relevant data.

In this study, blood samples, tongue coating specimens and fecal samples were used to explore. NMOSD The relevant mechanism of pain in patients and the mechanism of electroacupuncture in the treatment of pain in patients with optic neuromyelitis spectrum diseases, all samples will be frozen in the Biological Resources Center of Guangdong Provincial Hospital of Traditional Chinese Medicine and preserved. 3 The sample was destroyed after the study. All samples are only used for this study, and your relevant personal information will not be made public. Researchers, personnel of the Bioresource Center and the Ethics Committee will be allowed to have access to these samples, and

subjects can request withdrawal from the reservation or research of the sample at any time.

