[figure not shown]
9. Outcome evaluation indicators

Main evaluation indicators: NRS

Pain sheet rating

Secondary evaluation indicators: EDSS、MPQ Rating, SAS Anxiety Scale, SDS Depression Scale, SF-36 Quality of life scale, IL6、TNF- α 、fMRI Indicators.

10. Technology roadmap

11.2.1 Common adverse acupuncture events/Reaction and treatment: Acupuncture has adverse reactions such as hematoma, stagnation needle, halo needle, etc.

1) Spend money/Hematoma: During acupuncture and acupuncture, local bleeding caused by puncture of blood vessels./Hematoma. Mild bleeding/Of Patients with hematoma can use disinfectant cotton swabs or cotton balls for local compression to stop the bleeding without special treatment. Moderate and severe bleeding/Patients with hematoma should be based on their bleeding./Take corresponding measures to the degree of hematoma, first stop the bleeding to prevent the increase of local swelling, carry out local anti-inflammatory treatment, and ask a surgeon to assist in dealing with it.

2) Stagnation needle: When acupuncture the stagnation needle, you should first relax the local tense muscles, and gently take the needle. Do not pull it hard. It can be opened next to the stagnant needle. 2 Enter the needle inch by inch, and then take out the stranded acupuncture needle. Severe needle stagnation should be assisted by a surgeon.

3) Needle halo: When the patient pricks the needle with acupuncture, he should quickly take out the needle and let the patient lie flat, lower his head, cushion his footsteps, and moxibustion his Baihui acupuncture point. After the patient's halo needle situation is slightly relieved, he can be ordered to drink a little warm boiled water. If the patient's needle is serious and he or she can't wake up, it should be treated according to syncope.

4) Infection: When there is redness, swelling and heat pain in the acupuncture area, the patient's affected part is told to rest and move less to reduce the spread of pain and inflammation, raise the limbs, promote reflux, reduce swelling, do not squeeze the affected part, and carry out local anti-inflammatory treatment. If necessary, you should ask a surgeon to assist in dealing with it.

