11.3.2 Report of serious adverse events

When there is a serious adverse reaction, it should be reported to Guangzhou University of Traditional Chinese Medicine within 24 hours of the second affiliated hospital and fill in the form of serious adverse events.

12. Data management and statistical analysis

Measurement data use: average \pm Standard deviation, median (M), maximum value, Minimum value, matching is used for comparison in the counting data group. T Test (Or pairing symbol rank sum test), variance analysis is used for inter-group comparison (non-normal distribution and variance irregularity are tested by rank sum (Kruskal-Wallis)) and two comparison and calculation 95% CI. The quantitative main outcome indicators of multiple observation time points are analyzed by repeated measurement. Rank sum test is used for comparison between hierarchical data groups (Kruskal-Wallis). The counting data is expressed by composition ratio and rate, and the comparison of total efficiency groups is expressed by cal-square test (or Fisher Accurate probability method). Intergroup composition Compared with comparison 2 \times C Table or 3 \times C Table cal-square inspection.

13. Confidentiality

The results of the research through this project may be published in medical journals, but we will keep the patient's information confidential in accordance with the requirements of the law. Unless required by relevant laws, the patient's personal information will not be disclosed. If necessary, government administrations and hospital ethics committees and their relevant personnel can consult patients' information as required.

14. Ethical standards

The program of this experiment, Case report form, The informed consent form should be approved in writing by the Ethics Committee of Guangdong Provincial Hospital of Traditional Chinese Medicine before it can be carried out.

The researcher or person authorized by the researcher will be responsible for explaining the benefits and risks of participating in the trial to each patient, the legal representative of the patient or notary witness, and shall obtain the patient's written informed consent during the screening examination.

All original informed consent co-signed and signed by the subjects or their legal representatives and the person presiding over the PIC process shall be kept by the researcher.

15. Study schedules

Starting and ending date	Main research content	Expected results

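### Section 5.3 lists unauthorised drug use by patients already included as an exclusion; if applied to the NRS comparison, it selects patients after randomisation

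*Protocol*

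**What the plan says.** Protocol section 5 has three lists after the selection criteria. Section 5.2 gives conditions checked at entry. Section 5.4 gives the drop-outs: treatment not completed, poor compliance as judged by the researchers, and withdrawal. Between them, section 5.3 carries the same heading as 5.2 and has two items: "Incorrectly included in the case" and "Subjects took drugs that affected the relevant indicators of this study without authorization".

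Other sections bear on how 5.3 works:

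- **6.1:** the sample is 20, and "this study is an exploratory study".
- **6.2:** allocation envelopes are used in the order in which patients are included.
- **6.3:** "The study includes the blind design of patients and evaluators"; the acupuncture operator alone knows the allocation.
- **7, item 1:** "Patients record the daily intake and intensity of analgesic drugs required", in a daily diary.
- **8, treatment period:** "The electroacupuncture group will be treated with electroacupuncture on the basis of immunotherapy and basic analgesia"; the control group receives sham needling on the same basis.
- **8, visit after the eighth treatment:** NRS is collected on day 28 ± 3.
- **9:** "Main evaluation indicators: NRS".
- **12:** "The quantitative main outcome indicators of multiple observation time points are analyzed by repeated measurement". This section does not refer to 5.3 or 5.4.

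**The concern.** A rule that acts after randomisation and depends on what patients do can undo the balance that randomisation created. Here the trigger is use of drugs that affect the study's indicators, and the main indicator is pain. Extra analgesics are an obvious candidate, and more pain is a plausible reason to take them. If electroacupuncture works, more sham patients would then meet the rule. Removing them takes the worst scores mainly out of the sham arm.

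A second route does not need a treatment effect. The protocol does not say who decides that use was unauthorised, and one member of the team knows the allocation. If the rule is applied more readily in one arm, the arms differ for that reason alone.

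With 20 patients, each one excluded is 1/20 = 5% of the sample.

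**Working it through.** **Does 5.3 act after randomisation?** An incorrect inclusion can be found only in someone already included. The drug item speaks of subjects acting without authorisation, which presupposes enrolment. Entry exclusions and drop-outs have their own lists. Envelopes are used in order of inclusion (6.2), so an event after inclusion is in practice after allocation.

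**Does 5.3 remove data?** It states no consequence, and section 12 is silent on it. A second exclusion list for patients already included most naturally means removal, but that is a reading of the text.

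**Illustration of direction.** The protocol has no figure to reproduce: 6.1 gives 20 by reference to earlier studies, without effect size or SD. Apart from the total of 20, every input here is assumed.

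- Day-28 NRS if nobody took extra drugs: normal, mean 5.5 sham and 4.0 electroacupuncture (difference 1.5), SD s = 1.5 or 2.0, 10 per arm.
- A share p = 0.25, 0.5 or 1 of patients above a cut-off c = 6, 7 or 8 takes an unauthorised drug. This gives 3 × 2 × 3 = 18 cells.
- If such a patient is kept, the drug lowers NRS by d = 1, 2 or 3 points.

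For an arm with mean m, let a = (c − m)/s, let q be the normal upper tail at a, and let φ be the normal density.

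- Mean of those left after exclusion: m − p·s·φ(a)/(1 − p·q).
- Expected number excluded: 10·p·(q_sham + q_EA).
- Difference with everyone kept: 1.5 − d·p·(q_sham − q_EA).

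Example, s = 2, c = 7, p = 0.5:

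- Sham: a = 0.75, q = 0.2266, φ = 0.3011; mean left 5.5 − 0.3011/0.8867 = 5.160.
- Electroacupuncture: a = 1.5, q = 0.0668, φ = 0.1295; mean left 4.0 − 0.1295/0.9666 = 3.866.
- Difference after exclusion: 5.160 − 3.866 = 1.294, with 5 × 0.2934 = 1.47 of 20 patients excluded.
- Difference with everyone kept: 1.5 − 0.0799·d, which is 1.420, 1.340 and 1.260 for d = 1, 2 and 3.

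All 18 cells:

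| Handling | Difference (1.5 without extra drugs) | Cells below exclusion |
|---|---|---|
| Exclude (0.13 to 5.60 of 20 removed) | 0.784 to 1.467 | – |
| Keep all, d = 1 | 1.222 to 1.489 | 0 of 18 |
| Keep all, d = 2 | 0.944 to 1.478 | 4 of 18 |
| Keep all, d = 3 | 0.665 to 1.467 | 11 of 18 |

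If unauthorised use is rare, little happens: with s = 2, c = 7 and p = 0.1, exclusion gives 1.464 and removes 0.29 of 20.

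**No true effect (both arms at mean 5.5).** Equal application gives 0.00 in every cell. Now let 75% of those above the cut-off be removed in one arm and 25% in the other. With s = 2 and c = 7, the means left are 5.5 − 0.75·2·0.3011/(1 − 0.75·0.2266) = 4.956 and 5.5 − 0.25·2·0.3011/(1 − 0.25·0.2266) = 5.340, a false difference of 0.38. Over the three cut-offs and two SDs it runs from 0.08 to 0.61. The arm that loses more patients looks better.

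**The case against.** The strongest reply is that the protocol never says these patients leave the analysis. Section 5.3 sits under case selection and could mean stopping participation or marking a deviation. The text is a rough translation with a repeated heading, and an analysis plan that is not shown may define a full analysis set. A reader might infer that the protocol orders these data to be deleted, or that the lack of a named analysis set is itself the fault. The documents support neither. What stands is narrower: the protocol states an exclusion for included patients and sets no limit on its scope, so a later plan must either follow it or override it.

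The link to pain is also inferred. The item reaches only unauthorised use, basic analgesia continues in both arms, and analgesic intake goes in the diary. Some or most intake prompted by pain may be within the plan; the protocol does not draw the boundary. The frequency is unknown and could be close to nil.

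Blinding of patients and evaluators makes unequal application less likely. It does not stop selection that follows from pain itself, and it does not cover the operator.

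Finally, the trial is exploratory, and the illustration does not show that keeping everyone gives a larger estimate. Both points are right and limit the weight of the finding. The argument for change is that the randomised groups stay intact.

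**Conclusion.** The point holds in conditional form. Section 5.3 acts on randomised patients, one trigger can depend on the main outcome, and its natural reading is removal. If it is applied to the NRS comparison, the result is selection after randomisation.

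The direction depends on how the rule is applied. With equal application, drug use that follows pain and a true effect, the difference shrinks: 1.5 becomes 0.78 to 1.47 in the assumed grid. If the drug use is unrelated to pain, or there is no effect and application is equal, this mechanism gives no bias. With unequal application and no effect, a false difference of 0.08 to 0.61 points appears in the same model, in favour of either arm. A reader might infer that the rule can only hide an effect and carries no false-positive risk. That does not follow, because the protocol does not secure equal application.

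The figures rest on assumed means, SDs, cut-offs and shares, on equal arms, and on normal scores that ignore the limits of the scale. They show direction only. The actual size cannot be derived from the documents.

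**What to change.** - Reword 5.3 so that unauthorised drug use after randomisation is recorded as a protocol deviation and is not a ground for removal from the primary NRS analysis.
- Still collect the planned day 28 ± 3 NRS from these patients.
- Add a line to section 12: all randomised patients with NRS data are analysed in their assigned group. It should also cover patients found to be incorrectly included (5.3) and those meeting the 5.4 drop-out items, which raise the same question.
- Report diary analgesic use by arm.
- Use the 5.3 drug exclusion only in a sensitivity analysis, with each case decided blind to group.

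The cost is wording in 5.3 and section 12. No visit or patient is added, since the NRS assessment and the diary are already planned. The downside is that the estimate then includes the effect of any extra drugs. That is a different quantity from the effect without them, and it may be smaller than under exclusion, as in the 4 and 11 cells of the table. No position is taken on which drugs should be permitted.
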